Baseline assessment. Baseline assessments with patients and CFMs will be conducted by staff from the CASAA Program Evaluation Service (PES). Screening and baseline measures assess inclusion/exclusion criteria; locator and tracking information, sociodemographic descriptors, potential moderator variables; alcohol and other drug use, consequences, and diagnosis; CFM functioning and baseline measurement of hypothesized mediators of response to treatment (see Table 1). Each individual will be interviewed separately, and the patient and CFM may be scheduled at different or the same times for their baseline interviews. Patient baseline data collection will take approximately 2.5 hours; CFM baseline data collection will take approximately 1.25 hours. Patients will be compensated \$50; CFMs will be paid \$30.

Randomization. After the baseline interview, couples will be randomly assigned to TAU or TAU+B-FIT using urn randomization (Stout, Wirtz, Carbonari, & Del Boca, 1994) to balance groups on patient gender, severity of alcohol dependence, and type of CFM (parent versus partner versus other).

Treatment Conditions

Treatment as usual (TAU). Turquoise Lodge Hospital (TLH) provides detoxification services and residential treatment to adults with substance use disorders. The average residential stay is 18-21 days. TLH is currently developing an intensive outpatient program from which we also plan to recruit. **TAU at TLH consists of mainly group and some individual therapy.** Families do not typically participate in treatment but are allowed to visit patients during designated weekend hours.

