Given that our target population is substance abuse treatment patients and their family members, it is likely that many participants will be ethnic minorities, economically or educationally disadvantaged, or with trauma histories. Because we want our sample to be representative, it is justified that we include participants who may come from these groups, although such characteristics will not affect study inclusion or exclusion. There is the potential that pregnant women could participate in the intervention, although this will not be a concern given the non-invasive, low-risk nature of the study.

As previously stated, TLH patients may be involved in the criminal justice system insofar as they have been convicted for an alcohol related offense. We will make it very plain during informed consent that data collected as part of the research study will not be available to the courts and will have no bearing on their status with the courts. Because they are not prisoners they will not require special protections, but we still need to be mindful that simply being involved in the criminal justice system makes them more vulnerable than a group not involved in the criminal justice system. Further, only clients who have voluntarily admitted themselves (i.e., are not court-mandated) to treatment at TLH will be eligible for study participation.

Individuals receiving inpatient services may perceive decreased autonomy in their decision to participate in the study. As a precaution against this, we will recruit only patients who admitted themselves voluntarily to TLH's inpatient unit. More generally, it is possible that patients may believe they should participate to maintain good standing with their treatment providers. The recruitment and informed consent processes will clearly state that participation in the study intervention or subsequent withdrawal will have no impact whatsoever on their access to or course of treatment.

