percentage of days abstinent (PDA) and percentage of days of heavy drinking (PDH). We believe that this is a conservative estimate given the method in which the planned HLM handles missing data. In a two-tailed test adjusted for conducting correlated tests of drinking behavior over time ($\alpha = .05/2 = .025$), the baseline dependent measure entered as a fixed covariate and 1 *df* for the between-group term, we estimate that we will have .703 power to reject the null hypothesis of no difference between TAU and TAU + B-FIT with 51 participants and an effect size of .20 ($d = .25$ to achieve power of .80).

Statistical analyses. An extensive set of analyses is proposed that includes the assessment of treatment fidelity, document CFM and patient satisfaction with the B-FIT intervention, and examine outcomes in general, mechanisms of change, and potential moderators of treatment response. Initial attention will be directed to investigating overall and between-group attrition rates and distributions of key measures prior to conducting primary analyses. Although quantitative support will be provided in the achievement of all study Aims, the described statistical analyses will focus on the stated objectives in study Aim 2a, 2c, and 2d, which are central to the proposed model (Figure 1).

Aim 2a. Obtain estimates of the relative impact of B-FIT on patient treatment adherence, drinking outcomes, family functioning, and functioning of the CFM. Treatment adherence will be defined as the total number of TAU sessions attended between randomization and the 4-month follow-up interview (measured by the TSR and Form-90). Two primary alcohol use measures will be considered and aggregated into four monthly values: proportion abstinent days from alcohol (PDA: days abstinent/ 30 days) and percentage of days of heavy drinking (PDH). Family functioning will be assessed using the Cohesion and Conflict subscales of the Family Environment scale, and the Family Communication scale total score. CFM functioning will be defined as total scores on the Beck Depression Inventory (BDI) and Beck Anxiety Inventory (BAI).

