Generalized linear models (GLM) will assess the relative benefit of the B-FIT intervention to TAU alone on treatment adherence, family, and CFM functioning. Parameter estimates will be derived using maximum likelihood with robust estimators. In the treatment adherence GLM, two covariates are planned: number of TAU sessions attended *prior* to randomization and baseline PDA. The dependent measure will be the total number of TAU sessions attended from randomization to the 4-month follow-up and treatment assignment will be entered as a between-subject factor. A two-tailed test will be done with Type I error set at $\alpha = .05$. Four GLMs will be used to assess the relative benefit of B-FIT on family functioning; two using the patient 4-month report of family Cohesion and Conflict and two based upon CFM 4-month report of family Cohesion and Conflict. Baseline values of the two scales will be used as covariates. Treatment group will be entered into the model as a between-subject factor and Type I error will be adjusted to $\alpha = .05/2 = .025$ in the two-tailed tests. The relative benefit of B-FIT on CFM functioning will be determined using two GLMs. The first GLM will use 4-month BDI scores as the dependent measure and baseline values of the BDI will be entered as a covariate. Baseline values of PDA for the CFM also will be entered as a covariate to negate any influence of drinking on self-reported depression. Treatment assignment will be entered as a between-subject factor. A second GLM following the same strategy then will use the 4-month BAI score as the dependent measure. These tests of CFM functioning will be adjusted by $\alpha = .05/2 = .025$ to control for inflated Type I error.

The relative benefit of adding the B-FIT sessions to TAU on drinking over four months will be determined using two longitudinal hierarchical linear models, one for PDA and a second for PDH (Raudenbush & Bryk, 2002). Modeling of change in alcohol use will be restricted to the linear effect given the limited number of time points. The random intercept in the unconditional models will be examined first, followed by fitting the conditional models, which will introduce baseline value of the respective drinking measure (PDA or PDH) as a fixed covariate and the random linear time term. Treatment group will then be entered in level two of the model and will be tested via the *t*-statistic.

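### If outpatients are enrolled alongside residential patients, the adherence model should adjust for treatment program; the plan omits it and is inconsistent on whether outpatients are recruited at all

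*Combined protocol and SAP*

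**What the plan says.** **Sources of patients.** Under Treatment Conditions, Treatment as usual (TAU), the hospital is described as offering detoxification and residential treatment: "The average residential stay is 18-21 days". The same paragraph continues: "TLH is currently developing an intensive outpatient program from which we also plan to recruit". Under Human Subjects Interactions, Target Population, a paragraph on perceived autonomy states: "we will recruit only patients who admitted themselves voluntarily to TLH's inpatient unit".

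**Allocation.** The Randomization paragraph uses an urn "to balance groups on patient gender, severity of alcohol dependence, and type of CFM (parent versus partner versus other"). Program is not among the factors.

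**Outcome.** Data Analysis/Statistical Considerations, Aim 2a: "Treatment adherence will be defined as the total number of TAU sessions attended between randomization and the 4-month follow-up interview". The count is not scaled to the number of sessions offered.

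**Model.** For the adherence GLM, "two covariates are planned: number of TAU sessions attended *prior* to randomization and baseline PDA". Treatment assignment is the between-subject factor, tested two-sided at .05. Program is not a covariate, and Aim 2d does not name it among its moderator classes.

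**The concern.** Program is known before randomization and could be related to the outcome. A residential stay of 18-21 days fills only 15% to 17.5% of four 30-day months (18/120 and 21/120), and some of it has passed before randomization. An outpatient program would probably run on another calendar. A raw session count then combines how well a patient attends with how much was on offer.

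Prior sessions need not carry the same information as program. One prior count could belong to a residential patient close to discharge or to an outpatient who has just started.

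A baseline variable related to the outcome, left out of both the allocation and the model, adds its variance to the error term. The TAU arm is planned at 20 dyads at baseline and 17 analysed, so the trial has little precision to give away.

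**Working it through.** **Inputs from the plan.** The RCT target is 60 patients (Participant Enrollment), with 40 in B-FIT at baseline (Aim 2c), hence 20 in TAU. With 15% attrition (Statistical power), 40 x .85 = 34, 20 x .85 = 17 and 60 x .85 = 51, which reproduces the analysed numbers. The plan gives no power or effect size for adherence. Its only power figure, .703, concerns PDA and PDH, and nothing below depends on it.

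**Inputs assumed.** The documents give neither the outpatient share q nor the gap in mean sessions between programs, Delta, in within-program SDs. I take q = .10, .25, .50 and Delta = 0.5, 1, 2. The distribution and link of the GLM are not stated, so a linear model is used. Plain randomization stands in for the urn.

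**Step 1: chance imbalance.** The SD of the arm difference in outpatient share is about sqrt(q(1-q)(1/n1 + 1/n2)). At 34:17 and q = .50 this is sqrt(.25 x .0882) = .149; the exact hypergeometric value is .150. Exact probabilities of a gap of at least 20 percentage points:

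| q | 40:20 | 34:17 |
|---|---|---|
| .10 | 1% | 4% |
| .25 | 11% | 18% |
| .50 | 17% | 24% |

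**Step 2: standard error.** With program left in the error term, the SE is multiplied by sqrt(1 + q(1-q)Delta^2). Smallest case: sqrt(1 + .09 x .25) = 1.01. Largest case: sqrt(1 + .25 x 4) = 1.41. To show what this means for power, take an illustrative effect of 0.8 within-program SD, 34:17, two-sided .05. Power with program in the model is .77. Without it:

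| q | Delta | SE factor | Power |
|---|---|---|---|
| .10 | 0.5 | 1.01 | .76 |
| .10 | 1 | 1.04 | .73 |
| .10 | 2 | 1.17 | .64 |
| .25 | 0.5 | 1.02 | .75 |
| .25 | 1 | 1.09 | .70 |
| .25 | 2 | 1.32 | .53 |
| .50 | 0.5 | 1.03 | .74 |
| .50 | 1 | 1.12 | .67 |
| .50 | 2 | 1.41 | .48 |

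**Step 3: steps 1 and 2 are one loss, not two.** At 34:17 the base SE is sqrt(1/34 + 1/17) = .297. At q = .50 and Delta = 2, imbalance contributes an SD of about .149 x 2 = .297. Then sqrt(.297^2 + .297^2) = .42 = 1.41 x .297. The inflated SE already contains the chance imbalance.

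**Step 4: what prior sessions recover.** If prior sessions correlate r with program and otherwise do not predict the outcome, the factor becomes sqrt(1 + q(1-q)Delta^2(1 - r^2)). At q = .50 and Delta = 2 it is 1.41 (r = 0), sqrt(1.75) = 1.32 (r = .5) and sqrt(1.36) = 1.17 (r = .8). A simulation of the adherence model with prior sessions and PDA (4,000 runs per scenario) gave power without program of .44, .48 and .61 at these correlations, against .71-.74 with program.

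**Step 5: validity.** In the same simulations without program, type I error was .046-.054 and the estimated effect was unbiased on average.

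**The case against.** **The premise may not occur.** The outpatient program was still being developed. Besides the Target Population sentence, other text assumes inpatients: family members must come to visiting hours (Inclusion and Exclusion Criteria), benefits are tied to the inpatient stay (Benefits), and gift cards are held until discharge (Participant Compensation). This stands as a condition on the point. It does not remove it: the Target Population sentence can be read as a safeguard on voluntariness for inpatients, and the patient criteria require only that services are received at the hospital.

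**A reader might infer that program largely fixes how many sessions are available.** The documents do not support that. They give no session schedule for either program and no outpatient length, and they do not say whether sessions after residential discharge count as TAU. The Follow-up section expects some patients to be still in treatment then. A difference by program is plausible, not established.

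**A reader might infer that imbalance could shift the result by about the effect being sought.** No adherence effect is stated; the .20 and .25 in the power paragraph are for drinking outcomes. By step 3, a one-SD imbalance is at most about 0.7 of the SE without program in this range (.297/.42).

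**The loss may be small.** This stands for some scenarios: at a 10% share and a gap of 0.5-1 SD, power falls only from .77 to .73-.76. The planned prior-sessions covariate also recovers some of any loss.

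**The trial is developmental.** It emphasises estimating effect sizes. That limits the weight of a single test, but an inflated SE widens the interval around the adherence estimate just the same.

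**Conclusion.** The point holds as a conditional one about precision. The two recruitment statements conflict on a literal reading and must be reconciled. If no outpatients enter, the rest lapses.

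If they do enter, the adherence GLM omits a pre-randomization variable that plausibly predicts the session count, and prior sessions replace it only in part. Over the assumed range, the SE factor is about 1.01 to 1.41 before any help from prior sessions. Where the true value lies depends on the outpatient share and the program gap, neither of which the documents give.

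It would be wrong to conclude that the adherence comparison is biased or its test invalid. Randomization protects against average bias, and the simulated type I error stays at its nominal level.

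**What to change.** 1. Reconcile the Treatment as usual and Target Population sections, so that the plan states whether outpatients are recruited.
2. Record program (residential or intensive outpatient) for every dyad at randomization. For dyads already randomized, enter the program they were in at that time.
3. If any outpatients are enrolled, add program as a prespecified covariate in the Aim 2a adherence GLM. Study Timelines places analysis from December 2017, after this February 2017 version, so this can still be settled in advance.
4. Treat program as an urn factor only as an option. RCT recruitment was scheduled from October 2016, so the change could fall mid-recruitment, and a fourth factor slightly loosens balance on the other three. The covariate alone recovers most of the precision.

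Cost: one recorded field, one sentence and one degree of freedom. If few outpatients enter, the gain will be small.

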PES staff will obtain full informed consent at TLH in a one-on-one, private meeting. Prospective research participants will be apprised of all requirements of the study, including the sessions, the type of therapy, who will provide that therapy, the nature of the assessments, follow-up requirements, official records that will be reviewed, who is responsible for the study, and to whom the subject should go if they need information or help. The Consent Form also states that participating in the study will neither help nor hurt the participant's standing in any legal matters. Standard Consent form assurances are included, for example that the subject may withdraw from the study at any time with no harm to them or loss of services to which they are otherwise entitled. Consent forms will be signed by the prospective research participants (patients and CFM), and a research staff person and dated. In addition, a Federal Certificate of Confidentiality (FCC) has been obtained to ensure a higher level of protection for participant research data. Participants will be provided a copy of the consent form (see appended patient and CFM consent forms for both the pilot and RCT).

It is possible that patients or family members could be under the influence of alcohol or drugs during the consent process and therefore at diminished decisional capacity. Research staff obtaining consent will have the discretion to terminate the consent procedure if they have clear reason to believe the

person is intoxicated, either through positive breathalyzer results or overt behavior, as reliable biological assessment of acute non-alcohol drug intoxication is unavailable.

As an additional safeguard to ensure understanding during the consent process, the patient and family member consent forms will end with a brief quiz containing the following True/False questions: (1) I will be in 3 therapy sessions that include a family member and myself (True); (2) I will not be paid for my participation (False); and (3) My conversations during the therapy sessions will be recorded (True). The person obtaining consent will verbally address any incorrect responses with the participant and re-verify if the person understands the consent and wishes to participate.

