Research staff will obtain study informed consent and consent to contact the CFM. After informed consent, research staff will contact the CFM to describe the study and conduct an initial screening. CFMs will be screened in person or over the phone by study personnel. At the beginning of the screening, the staff member will clarify, "Now I am going to ask you a few short questions about your alcohol and drug use, your relationship to your family member, and your own psychological state to see if you and your family member are eligible for this study. If you do not want to answer a question that is fine and we can end our conversation at that point." A simple checklist will be used to assess family member age, frequency of contact with the patient, and current help-seeking status. Presence of domestic violence will be assessed using the Partner Violence Screen (Feldhaus et al., 1997). Psychotic symptoms will be assessed using the psychotic screening questions from the SCID (<http://www.scid4.org>). Severity of alcohol use will be assessed with the AUDIT (Saunders, Aasland, Babor, de la Fuente, & Grant, 1993); a score of 8 or greater will exclude the CFM from the study. Severity of drug dependence will be assessed with the DAST-10 (Skinner, 1982); a score of 3 or greater will exclude the CFM. If eligible, the family member will be provided with a brief description of the study, and asked about willingness to participate. If ineligible, the family member will be offered referrals for other treatment programs (we will only do this with family, as the patients will already be in treatment).

If the family member is willing to participate and meets all screening criteria, the research staff member will meet with the family member, complete the informed consent, and collect baseline study data. After the CFM has provided informed consent, the research staff member will collect baseline data from the patient.

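### The consent quiz keys three family sessions as True for all participants, but RCT dyads consent before randomization and about one third are assigned to TAU without these sessions

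*Combined protocol and SAP*

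**What the plan says.** Consent Procedures (Study Design and Procedures, III) refers to consent forms for both phases ("see appended patient and CFM consent forms for both the pilot and RCT"). It then states that "the patient and family member consent forms will end with a brief quiz containing the following True/False questions". Three items follow with a single answer key:

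- Item 1: "1) I will be in 3 therapy sessions that include a family member and myself (True").
- Item 2 concerns payment and is keyed False.
- Item 3: "3) My conversations during the therapy sessions will be recorded (True").

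On wrong answers, the section says "The person obtaining consent will verbally address any incorrect responses with the participant" and then checks again that the person understands and wishes to take part. Target Population (Human Subjects Interactions, I) mentions the quiz a second time, also without distinguishing the two phases.

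The order of events is given elsewhere. Recruitment and Screening Procedures has staff obtain the patient's consent, then meet the family member to "complete the informed consent, and collect baseline study data", and then collect the patient's baseline data. The Randomization paragraph says: "After the baseline interview, couples will be randomly assigned to TAU or TAU+B-FIT using urn randomization". Under Treatment Conditions, the three joint sessions appear only in the TAU + B-FIT description. The TAU description says that families are not usually part of treatment and may visit at weekends.

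**The concern.** The quiz is presented as a further safeguard for understanding. For the RCT its first item asks people to affirm something that depends on an assignment not yet made. A participant who has grasped the design has no correct option. True overstates what is promised, and False, chosen because TAU alone is possible, is scored as an error. None of the three listed items asks whether the person knows that treatment is decided by chance, which is the main way in which the RCT differs from the pilot.

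What is at stake is the quality of the comprehension check. The protocol itself is cautious about perceived coercion and reduced decisional capacity in this population. The study schedule places the pilot in October to December 2015 and RCT recruitment from October 2016 to June 2017, and this version is dated February 12, 2017. On that schedule, the people still to take the quiz are RCT participants.

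**Working it through.** **Step 1. Does each keyed answer hold in each setting?** The settings come from Study Design, Treatment Conditions, Treatment fidelity and Participant Compensation.

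| Item | Key | Pilot | RCT, TAU + B-FIT | RCT, TAU |
|---|---|---|---|---|
| 1. Three family sessions | True | Holds | Holds, but unknown at consent | False |
| 2. Not paid | False | Holds | Holds | Holds (baseline and follow-up are paid) |
| 3. Therapy sessions recorded | True | Holds | Holds, but unknown at consent | Holds only if read as conditional on having study sessions |

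Item 1 fails outright for TAU. Item 3 is weaker: the recordings described are of B-FIT sessions rated for fidelity, and no recording of TAU therapy is described. Even so, the item can be read as applying only to those who have such sessions.

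**Step 2. Is the arm known when the quiz is taken?** Patient consent → family-member consent → baseline for both → randomization. The arm is never known at the quiz.

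**Step 3. How many dyads does this affect?** The Randomization paragraph states no allocation ratio, so the share has to be inferred.

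- Inputs: 60 RCT patients (Participant Enrollment); 40 in B-FIT at baseline (Data Analysis, Aim 2c); 34 B-FIT and 17 TAU after 15% attrition (Statistical power).
- TAU at baseline: 60 − 40 = 20.
- Reproducing the plan's own figures: 40 × 0.85 = 34 and 20 × 0.85 = 17, total 51. Both arms match.
- TAU share: 20/60 = 17/51 = 1/3.
- On these figures the item 1 key is false for 20 of 60 dyads, or 2 × 20 = 40 of 120 people.

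Participant Enrollment uses a different base. It treats 60 dyads as completers and allows up to 150 RCT participants: 120/(1 − 0.20) = 150, or 75 dyads. If the one-third share is kept, 75/3 = 25 dyads, or 50 of 150 people.

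**Step 4. Is there other single-arm wording?** Participant Enrollment describes all 60 RCT dyads as completing the three-session treatment. TAU dyads cannot do that. This fits pilot wording carried over into the RCT, although it does not prove it.

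**The case against.** The strongest reply is that the consent forms are an appendix that was not available for this review. The protocol cites forms for each phase, and the RCT form may already carry an adapted quiz or explain assignment clearly. This limits what can be said about the actual form. It does not rescue the protocol text, which prints one key for both phases and would then misdescribe its own form.

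Three stronger readings are tempting, and the documents do not support them.

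- *That consent as a whole is misinformed.* The quiz supplements a one-on-one consent meeting that is meant to cover all study requirements. The list of topics in Consent Procedures does not name random assignment, but it is not presented as exhaustive.
- *That staff talk people who understood out of a correct belief.* The text says only that incorrect answers are addressed and understanding is checked again. That conversation could equally be where assignment is explained. What stands is that the key classes the answer as incorrect.
- *That the quiz sets up disappointment and selective dropout in TAU.* The protocol gives no arm-specific attrition and no link from quiz wording to dropout. Disappointment with the control arm can arise in any open add-on trial, and B-FIT dyads carry a session burden of their own. The plan also examines between-group attrition before the primary analyses, keeps following those who withdraw from treatment, and uses a locator form and paid follow-up.

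**Conclusion.** The point stands as an error in the consent quiz as the protocol describes it. For the RCT, the keyed answer to item 1 is not knowable at consent. It is false for about one third of dyads: 20 of 60, or 25 of 75 at maximum recruitment. Item 3 has a milder form of the same fault, and none of the listed items covers random assignment.

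Two assumptions carry this. The first is that the RCT form uses the quiz as printed; if it does not, the error lies in the protocol's description and still needs correcting. The second concerns only the size: the one-third share comes from the planned arm sizes, since no ratio is stated, and the 25 of 75 figure assumes that the share holds at maximum recruitment.

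A reader might infer bias in the B-FIT versus TAU comparison through differential dropout. The documents neither support nor quantify that, and the conclusion does not rely on it.

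**What to change.** For the RCT consent forms:

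- Replace item 1 with: *I will be assigned by chance, and may or may not have 3 therapy sessions with my family member (True).*
- Replace item 3 with: *If I am assigned to the family sessions, they will be recorded (True).*
- Keep the present wording for the pilot only, and state in Consent Procedures which quiz belongs to which phase.
- Re-verify understanding with anyone who consented under the present key and has not yet been randomized.

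If the appended RCT form already uses different items, amend Consent Procedures to match it.

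The cost is a minor consent-form and protocol wording amendment to the IRB, plus a short conversation with any dyads awaiting randomization. Sample size, staffing and data collection do not change.
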